13.1. Data Collection Methods

The data will be transcribed from the subjects' source documents into the CRF approved by BioCryst. The data collection methods may be either a paper CRF or an electronic CRF, at BioCryst's discretion. All documentation supporting the CRF data, such as laboratory or hospital records must be readily available to verify entries in the CRF.

To ensure subject confidentiality, any documents (including laboratory reports, hospital records subsequent to SAEs, etc.) transmitted to BioCryst should not carry the subject's name.

13.2. Statistical Analysis Plans

A SAP will be created and approved prior to the review of any data. This document will provide a more technical and detailed description of the proposed data analysis methods and procedures.

13.3. Study Hypothesis

There are no hypotheses to be formally tested in this study.

13.4. Sample Size Estimates

The study is designed to evaluate the safety, pharmacokinetics, and effectiveness of IV administration of peramivir compared to oral oseltamivir in pediatric subjects with acute uncomplicated influenza. The sample size is not based on statistical considerations, rather a sample size of up to 140 subjects (approximately 117 randomized to peramivir) is considered adequate to evaluate the stated objectives.

13.5. Analysis Populations

The populations defined for analysis will include the intent-to-treat (ITT) population, intent-to-treat infected (ITTI) population, safety population, and an exposure-response population. Additional analysis populations may be defined to evaluate study results. Any additional analysis populations will be defined in the SAP.

- Intent-To-Treat Population: The ITT population will include all subjects who are randomized. The ITT population will be used for analyses of accountability and demographics.
- Intent-To-Treat Infected Population: The ITTI population will include all subjects who are enrolled, treated, and have influenza confirmed by RT-PCR. The ITTI population will be used for analyses of effectiveness.
- Safety Population: The safety population will include all subjects who received at least one dose of study drug. This population will be used for all safety analyses.
- Exposure-Response Population: The exposure-response population will include all subjects in the ITTI population who have a quantifiable plasma concentration of peramivir and at least one post-baseline effectiveness assessment. This population will be used for all exposure-response analyses.

13.6. End of Study Analysis

A final analysis is planned to occur after the last subject completes or discontinues the study, and the resulting clinical database has been cleaned, quality checked, and locked.

13.7. General Issues for Statistical Analysis

13.7.1. Multiple Comparisons and Multiplicity

No adjustments are currently planned.

13.7.2. Covariates

Not applicable.

13.7.3. Planned Subgroups

Analyses will be displayed by age group and viral subtype at Screening.

13.7.4. Missing Data

Every effort will be made to obtain required data at each scheduled visit from all subjects who have been randomized. In situations where it is not possible to obtain all data, it may be necessary to impute missing data. In assessing the time to event endpoints, subjects who withdraw or never achieve resolution/alleviation, missing data will be censored using the date of subject's last non-missing assessment. Additional details on the handling of missing data will be presented in the SAP.

13.8. Effectiveness

13.8.1. Effectiveness Endpoints

All effectiveness endpoints will be summarized using descriptive statistics by treatment group, age group, and study day/time, if appropriate.

13.8.2. Effectiveness Analyses

Time to resolution of fever, defined as a temperature < 99.4 oral or < 98.4 axillary with no antipyretic medications taken for at least 12 hours, will be estimated for each age group and overall by treatment group using the method of Kaplan-Meier. Subjects who do not achieve resolution of fever will be censored at the time of their last assessment.

Time to resolution of influenza symptoms, defined as the time from initiation of study drug until the start of the 21.5-hour period (24 hours- 10%) where all symptoms of influenza are recorded as none or mild, will be estimated for each age group and treatment group using the method of Kaplan-Meier. Subjects who do not experience alleviation of symptoms will be censored at the time of the last non-missing symptom assessment. As the number and type of symptoms varies by age, the analysis of time to resolution of symptoms will not be presented as an overall assessment.

Reduction in viral shedding will be assessed as the change from baseline in log₁₀ TCID₅₀/mL and RT-PCR, and will be summarized for each age group, treatment group and study visit.

Changes in virus susceptibility to neuraminidase inhibitors between virus cultured at Baseline and the last post-treatment sample from which virus can be cultured will be assessed using virology laboratory tests. Virology laboratory tests will include phenotypic characterizations of influenza virus recovered (hemagglutinin and neuraminidase) and viral susceptibility to peramivir, and genotypic analysis of primary virus isolates. These analyses will be presented separately by age group and viral subtype.

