Following treatment on study Day 1, subjects will undergo follow-up assessments on Days 3, 7, and 14. The Day 3 visit may be a home visit (performed by a qualified study nurse). Day 7 is required to take place in the clinic, and Day 14 may either be a clinic visit, home visit, or follow-up phone call to the subject/parent/guardian.

All parents/caregivers will record the following information in the Subject Diary:

- Temperature measurements (oral or axillary) will be taken with an electronic thermometer provided by BioCryst, approximately every 12 hours until temperature normalizes for 48 hours (i.e., temperature without antipyretic is < 99.4 orally in children ≥ 6 and < 98.4 axillary in children < 6 years old for 4 measurements). With the exception of the baseline measurement, all temperature measurements will be obtained at least 4 hours after, or immediately before, administration of oral acetaminophen or other antipyretic medications, if taken.
- Date and time of oral oseltamivir dose administration, if applicable. This should be recorded in the Subject Diary twice a day for 5 days.
- Doses of antipyretic medication and any medications taken for symptomatic relief, each day through the last follow-up assessment.
- The ability of the child or adolescent to return to day care/school and/or resume their normal "pre-illness" daily activity.
- The child or adolescent's appetite and eating patterns assessed as normal or reduced/abnormal.

All parents/caregivers of subjects 7 years of age and older will record the following additional information in the Subject Diary:

• Assessment of 7 influenza symptoms [cough, sore throat, nasal obstruction, myalgia (muscle aches), headache, feverishness, and fatigue] on a 4-point severity scale (0, absent; 1, mild; 2, moderate; 3, severe) twice daily, beginning pre-dose on Day 1 until symptom resolution or through the last follow-up visit, (whichever comes first).

All parents/caregivers of subjects \geq 4 years of age to \leq 6 years of age will record the following additional information in the Subject Diary:

• Assessment of 7 influenza symptoms [cough, sore throat, nasal obstruction, headache, feverishness, fatigue/malaise, and gastrointestinal symptoms (nausea, vomiting or diarrhea)] on a 4-point severity scale (0, absent; 1, mild; 2, moderate; 3, severe) twice daily until symptom resolution or through the last follow-up visit, (whichever comes

first).

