All parents/caregivers of subjects ≤ 3 years of age will record the following additional information in the Subject Diary:

• Assessment of 5 influenza symptoms [cough, rhinitis, feverishness, malaise alternating with irritability and gastrointestinal symptoms (nausea, vomiting or diarrhea)] on a 4-point severity scale (0, absent; 1, mild; 2, moderate; 3, severe) twice daily, beginning pre-dose on Day 1 until symptom resolution or through the last follow-up visit, (whichever comes first).

An adequate nasal swab specimen will be collected from all enrolled subjects at Baseline (pre-dose) for virus sub-type identification and quantitative virologic assessments and at the follow-up assessments on study Days 3, 7, and where possible on Day 14.

Specimens from all subjects yielding influenza virus will also be assessed for susceptibility to neuraminidase inhibitors (Day 1 and last specimen yielding influenza virus on culture). A central laboratory will perform all virologic assessments.

Plasma samples for determination of drug concentration on subjects randomized to peramivir will be drawn as follows:

Up to 4 blood samples will be drawn, where possible, during the following time periods, beginning from the end of dosing until release from the site:

- One time point immediately following completion of the infusion
- One time point from 30 minutes to 1 hour post-infusion
- One time point from 1 hour to 3 hours post-infusion
- One time point from 3 to 6 hours post-infusion

Note: Subjects ≥ 5 kg will have four 1.0 mL blood draws at the above stated sampling times. Subjects < 5 kg will have two 1.0 mL blood samples; one time immediately following completion of the infusion and one time between 1-3 hours post-infusion. Adverse events and concomitant medications will be monitored at each scheduled visit from the Screening/Baseline assessment to final study visit. Clinical laboratory investigations (chemistries, hematology, and urinalysis) will be collected at Baseline and at the Day 7 visit. Safety and tolerability will be evaluated through assessments of adverse events, laboratory analyses (clinical chemistry, hematology, and urinalysis), vital signs and physical examinations at the time points indicated in the schedule of assessments.

Number of subjects (planned):

Up to 140 subjects will be enrolled in this study according to the following age groups:

- Birth to < 28 days: up to 10 subjects will receive IV peramivir

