- Doses of antipyretic medication and any medications taken for symptomatic relief, each day through the last follow-up assessment.

- The ability of the child or adolescent to return to day care/school and/or resume their normal "pre-illness" daily activity will be assessed once daily until the child or adolescent returns to day care/school and/or resume normal "pre-illness" daily activity.
- The child or adolescent's appetite and eating patterns assessed as normal or reduced/abnormal will be assessed once daily until they return to normal "pre-illness" level.

All parents/caregivers of subjects 7 years of age and older will record the following additional information in the Subject Diary:

• Assessment of 7 influenza symptoms (cough, sore throat, nasal obstruction, myalgia [muscle aches), headache, feverishness, and fatigue) on a 4-point severity scale (0, absent; 1, mild; 2, moderate; 3, severe) twice daily, beginning pre-dose on Day 1 until symptom resolution or through the last follow-up visit, (whichever comes first).

All parents/caregivers of subjects ≥ 4 years of age to ≤ 6 years of age will record the following additional information in the Subject Diary:

• Assessment of 7 influenza symptoms [cough, sore throat, nasal obstruction, myalgia (muscle aches), headache, feverishness, fatigue/malaise, and gastrointestinal symptoms (nausea, vomiting or diarrhea)] on a 4-point severity scale (0, absent; 1, mild; 2, moderate; 3, severe) twice daily, beginning pre-dose on Day 1 until symptom resolution or through the last follow-up visit, whichever comes first.

All parents/caregivers of subjects \le 3 years of age will record the following additional information in the Subject Diary:

• Assessment of 5 influenza symptoms [cough, rhinitis, feverishness, malaise/irritability and gastrointestinal symptoms (nausea, vomiting or diarrhea)] on a 4-point severity scale (0, absent; 1, mild; 2, moderate; 3, severe) twice daily, beginning pre-dose on Day 1 until symptom resolution or through the last follow-up visit, (whichever comes first).

An adequate nasal swab specimen will be collected from all enrolled subjects at Baseline (pre-dose) for virus sub-type identification and quantitative virologic assessments and at the follow-up assessments on study Days 3, 7, and where possible Day 14.

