10.3.2. Influenza Signs and Symptoms

Subjects (or parent/guardian) will be asked to provide an assessment of influenza symptoms on a 4-point severity scale (0, absent; 1, mild; 2, moderate; 3, severe) beginning pre-dose on Day 1 until symptom resolution and through the last follow-up visit, (whichever comes first). These assessments will be recorded on each day that the medical condition allows. Study staff will obtain this assessment pre-dose and post-dose on Day 1, and the subject's trained parent-guardian will then obtain it until returning to the site for the final visit. Influenza signs and symptoms vary by age. In addition, younger children may not be able to verbalize specific symptoms. Therefore, the assessment of influenza symptoms will be based on the subject's age, as follows:

- Parent/guardian of subjects birth to ≤ 3 years of age will provide/record an assessment of 5 influenza symptoms [cough, rhinitis, feverishness, malaise/irritability and gastrointestinal symptoms (nausea, vomiting or diarrhea)]
- Subjects ≥ 4 years of age to ≤ 6 years of age will be asked to provide an assessment of 7 influenza symptoms [cough, sore throat, nasal obstruction, myalgia (muscle aches), headache, feverishness, and gastrointestinal symptoms (nausea, vomiting or diarrhea)].
- Subjects 7 years of age and older will be asked to provide an assessment of 7 influenza symptoms (cough, sore throat, nasal obstruction, myalgia (muscle aches), headache, feverishness, and fatigue).

During the first visit, the study staff will instruct the parent/care giver on completing these assessments and recording responses directly into the Subject Diary. Although the parent/care giver will be recording the responses, the subject should be involved in the assessment of the symptoms.

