13. STATISTICS

Descriptive statistical methods will be used to summarize the data from this study. Data will be summarized by treatment group, age group, and study day/time, if appropriate. Unless stated otherwise, the term "descriptive statistics" refers to number of subjects (n), mean, median, standard deviation (SD), minimum, and maximum for continuous data and frequencies and percentages for categorical data. The term "treatment group" refers to treatment assignment: single dose peramivir IV or oseltamivir BID for 5 days. The term "age group" refers to the following: 0-28 days; 28 days -<2 years, ≥ 2 years -<7 years, ≥ 7 years -<13 years, and ≥ 13 years -<18 years. All data collected during the study will be included in data listings. Unless otherwise noted, the data will be sorted first by treatment group, age group, subject number, and then by date within each subject number.

The statistical analyses will be conducted with the SAS® software package version 9.2 or higher. All analyses will be subject to formal verification procedures. Specifically, results will be verified utilizing independent programming prior to issuance of the draft statistical report. All documents will be verified by the lead statistician to ensure accuracy and consistency of analyses.

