# **Alleviation of Symptoms**

A subject has Alleviation of Symptoms if all of the assessed symptoms of influenza assessed on his/her subject diary based on age are either absent or are present at no more than mild severity level and at this status for a 21.5 hour (24 hours -10%) period.

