#### 6. STATISTICAL METHODS

Descriptive statistical methods will be used to summarize the data from this study. Data will be summarized by treatment group, age group, and study day/time, if appropriate. Unless stated otherwise, the term "descriptive statistics" refers to number of subjects (n), mean, median, standard deviation (SD), minimum, and maximum for continuous data and frequencies and percentages for categorical data. The term "treatment group" refers to randomized treatment assignment: single dose peramivir IV or oseltamivir BID for 5 days. The term "age group" refers to the following: 28 days - < 2 years,  $\ge$  2 years - < 7 years,  $\ge$  7 years - < 13 years, and  $\ge$  13 years - < 18 years. All data collected during the study will be included in data listings. Unless otherwise noted, the data will be sorted first by treatment group, age group, subject number, and then by date within each subject number.

The statistical analyses will be conducted with the SAS® software package version 9.2 or higher. All analyses will be subject to formal verification procedures. Specifically, results will be verified utilizing independent programming prior to issuance of the draft statistical report. All documents will be verified by the lead statistician to ensure accuracy and consistency of analyses.

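### The 4-6 year symptom list that defines alleviation is stated in three conflicting versions, and the 2 to <7 year analysis group mixes two diaries.

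*Protocol*

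**What the plan says.** **Event.** SAP 4.3.8 counts a child as alleviated when "all of the assessed symptoms of influenza assessed on his/her subject diary based on age are either absent or are present" only mildly, and this has to hold for 21.5 hours. Protocol 13.8.2 uses the same rule.

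**Analysis groups.** Protocol 13 lists, among others, "28 days -<2 years, ≥ 2 years -<7 years, ≥ 7 years -<13 years". SAP 6 also has a single "2 years - < 7 years" group. Both documents estimate time to alleviation by Kaplan-Meier for each age group and treatment group. Protocol 13.8.2 rules out an all-ages estimate: "the number and type of symptoms varies by age, the analysis of time to resolution of symptoms will not be presented as an overall assessment".

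**Diary, age 3 and under.** The Protocol synopsis has "Assessment of 5 influenza symptoms [cough, rhinitis, feverishness, malaise alternating with irritability and gastrointestinal symptoms (nausea, vomiting or diarrhea"). SAP 2.1 also gives five symptoms for children under 4.

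**Diary, ages 4-6.**
- Protocol synopsis: "Assessment of 7 influenza symptoms [cough, sore throat, nasal obstruction, headache, feverishness, fatigue/malaise, and gastrointestinal symptoms (nausea, vomiting or diarrhea").
- Protocol 10.1: "Assessment of 7 influenza symptoms [cough, sore throat, nasal obstruction, myalgia (muscle aches), headache, feverishness, fatigue/malaise, and gastrointestinal symptoms (nausea, vomiting or diarrhea"). SAP 2.1 gives the same eight items and also calls them seven.
- Protocol 10.3.2: "7 influenza symptoms [cough, sore throat, nasal obstruction, myalgia (muscle aches), headache, feverishness, and gastrointestinal symptoms (nausea, vomiting or diarrhea").

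**Enrolment.** Protocol 7.2 caps ages 2 to <4 at 10 children and ages 4 to <7 at 30. SAP 2.1 has one cohort of up to 40.

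**The concern.** Under an every-symptom rule, adding or removing one item changes who has had the event and when. If the plan does not fix the list, a programmer or reader cannot tell from the documents what the 4-6 year median measures.

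Pooling raises a related problem. The protocol declines to combine ages because the diaries differ, then combines two diaries inside one age group. That group's Kaplan-Meier curve mixes two event definitions, in proportions set by enrolment. Having separate diaries is deliberate and reasonable, since Protocol 10.3.2 notes that younger children may be unable to describe their symptoms. The objection is only to merging them in one estimate without showing the parts.

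The same difference affects the Composite Symptom Score, which SAP 4.3.8 defines as a raw sum over the age-appropriate items. SAP 6.1 summarizes its initial value for the ITT population without saying that diary versions are kept apart.

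**Working it through.** **1. Item count for ages 4-6**

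| Item | Synopsis | Protocol 10.1 and SAP 2.1 | Protocol 10.3.2 |
|---|---|---|---|
| Cough | yes | yes | yes |
| Sore throat | yes | yes | yes |
| Nasal obstruction | yes | yes | yes |
| Headache | yes | yes | yes |
| Feverishness | yes | yes | yes |
| Gastrointestinal | yes | yes | yes |
| Myalgia | **no** | yes | yes |
| Fatigue/malaise | yes | yes | **no** |
| Items listed | 7 | 8 | 7 |
| Count stated | 7 | 7 | 7 |

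The stated 7 reproduces in the synopsis and Protocol 10.3.2, and fails in Protocol 10.1 and SAP 2.1. That makes three distinct lists in four places, with six items common to all.

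**2. Effect on the event.** A child whose only remaining symptom is moderate myalgia is alleviated on the synopsis list and on no other. A child whose only remaining symptom is moderate fatigue/malaise is alleviated on the Protocol 10.3.2 list and on no other.

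**3. Which groups cross a diary boundary.** All groups under 2 years use the 5-item diary, and both groups from 7 years up use one 7-item diary. Only 2 to <7 spans two. At full caps the mix is 10/(10 + 30) = 25% on five items and 75% on seven or eight. Only cough, feverishness and gastrointestinal symptoms carry the same name in the 5-item list and in every 4-6 year list.

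**4. Size of the pooling effect.** The documents do not give the difference between the two event definitions in this trial. The nearest analogue is the Japanese pediatric peramivir study in Protocol 5.3.2.1. Its median was 27.9 h (95% CI 21.7-31.7) on cough, nasal discharge and temperature, and 30.5 h (22.6-45.8) when sore throat, headache, myalgia/arthralgia and fatigue were also counted. The ratio is 30.5/27.9 = 1.09.

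Assume exponential times and a 10:30 mix, and let r be the 4-6 year median divided by the 2-3 year median. In units of the 2-3 year median, the pooled median t solves

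0.25 × 2^(−t) + 0.75 × 2^(−t/r) = 0.5

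| r | t | Against 2-3 median | Against 4-6 median |
|---|---|---|---|
| 0.9 | 0.924 | −7.6% | +2.6% |
| 1.0 | 1.000 | 0% | 0% |
| 1.09 (30.5/27.9) | 1.069 | +6.9% | −2.2% |

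Values of r below 1 cannot be excluded. The Protocol 10.3.2 list has no malaise item and the 5-item list does, so on that version the older list does not simply contain the younger one.

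A second illustration, also assumed, takes all symptoms as exponential with equal medians. If they are independent, the median of the slowest of k symptoms is −log2(1 − 0.5^(1/k)), which is 2.95 for k = 5, 3.41 for k = 7 and 3.59 for k = 8. The ratios to five items are 1.16 and 1.22. With strongly correlated symptoms (0.9) they fall to 1.06 and 1.09, and with perfect correlation to 1.00. Choosing eight items over seven for ages 4-6 moves the median by 0% to 5%.

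**5. Composite score.** At 3 points per item the maximum is 5 × 3 = 15, 7 × 3 = 21 or 8 × 3 = 24, depending on the diary.

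**6. Precision if the group is split.** With uncensored times, order-statistic intervals for the median from Binomial(n, 0.5) are:
- n = 10: 2nd to 9th value, coverage 97.9%
- n = 30: 10th to 21st, 95.7%
- n = 40 pooled: 14th to 27th, 96.2%

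**The case against.** The case for leaving the analysis alone is fair. The 2 to <7 group is the defined analysis group in both documents, a single cohort in SAP 2.1, and a level of the stratification factor in SAP 4.3.1. Protocol 13.3 states that nothing is formally tested. Protocol 13.8.2 excludes only an all-ages estimate; it does not require each group to share one diary. SAP 6.2.2 plans individual-symptom estimates, and Listing 16.2.6.2 shows symptoms by subject. A 2 to <4 row would hold at most 10 children.

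Most of this stands as a reason to keep the pooled row and not to overstate the effect. It does not resolve the conflicting lists, and the individual-symptom curves help only for the items that both diaries share.

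Four stronger readings are tempting and are not supported:
- **The pooled median describes neither age band.** With r = 1.09 or 0.9 it lies within about 3% of the 4-6 year median.
- **The longer list must lengthen the time.** The Protocol 10.3.2 version leaves the direction open.
- **The endpoint cannot be computed.** SAP 4.3.8 ties it to the child's own diary, so it can; what the documents fail to settle is what that diary contained.
- **The comparison with oseltamivir is biased.** Oseltamivir children under 7 come only from before amendment 3, so the age mix could differ by arm, but the documents give no counts by arm and age band.

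**Conclusion.** Both parts hold. The conflict over the 4-6 year list is exact and rests on no assumption: three versions in four places, under a rule that makes the list the event. The mixing of two diaries in the 2 to <7 group is also certain, and it is inconsistent with the protocol's own reason for withholding an all-ages estimate.

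The numerical consequence is probably small: about 2% below the 4-6 year median and 7% above the 2-3 year median if the analogue study's ratio carried over, with the signs reversed if r is below 1. These figures assume exponential times and full caps. They borrow a ratio with wide intervals from a study that defined alleviation differently, so they are context and not an estimate for this trial. Because the endpoint is secondary and descriptive, no error rate or power is affected. The point is worth correcting because the descriptive medians are themselves the reported result.

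**What to change.** 1. Reconcile the 4-6 year list and its count in the Protocol synopsis, Protocol 10.1, Protocol 10.3.2 and SAP 2.1 to the diary actually used.
2. Keep the pre-specified 2 to <7 row, and add 2 to <4 and 4 to <7 rows beside it in the time-to-alleviation outputs: Table 14.2.2.1.1.1, Figures 14.2.2.1.1.2 and 14.2.2.1.1.3, and the viral-subtype outputs Table 14.2.2.1.2.1 and Figure 14.2.2.1.2.2. The cut at age 4 is already the enrolment boundary in Protocol 7.2, so it is not data-driven.
3. Summarize the Initial Composite Symptom Score by diary version and do not pool it across versions.

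The cost is wording plus extra descriptive rows or panels, with no new data. The drawback is small cells: at most 10 and 30 children over both arms, before restriction to RT-PCR-confirmed infection. At 4:1 that is at most about 10/5 = 2 and 30/5 = 6 on oseltamivir, and fewer because that randomization stopped, so there may be none aged 2-3. Keeping the pooled row preserves its precision.
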